APPENDIX C: PLAQUE PROTOCOL

CO-OP Chicago Plaque Protocol

This protocol was developed jointly between the CO-OP Chicago and UCSF investigators. The UCSF Coordinating Center is developing a calibration protocol for this measure for the Oral Health Disparities in Children Consortium (OHDC).

Background

Dental plaque is a biofilm that contains varying levels of cariogenic bacteria based on inherent microbiota and plaque age. The accumulation of dental plaque has been widely described in the literature as a significant risk factor for caries. Dental plaque on primary incisors is strongly predictive of future caries.¹ Most preventive behaviors emphasize removal of dental plaque to disrupt the cariogenic microbiota in the oral environment.

Many plaque scoring systems have been described in the literature, but none are specific to pediatric patients.² Plaque systems explored for this study include the Oral Hygiene Index, Silness-Löe Index, Simplified Oral Hygiene Index (OHI-S) and the Quigley-Hein Index with Turesky Modification.³ Due to age, cooperation potential, and the eruption status of primary teeth, traditional scoring systems which include permanent teeth are not applicable to the 0 to 3-year-old population and require modifications before epidemiologic use.

[figure not shown]
Simplified Oral Hygiene Index – Maxillary Incisor Scale (OHI-MIS)

The Simplified Oral Hygiene Index (OHI-S)⁴ will be modified for use in young children with primary teeth, to assess the status of current oral hygiene, based on the amount of debris (plaque) present. The original Oral Hygiene Index (1960) scored 12 tooth surfaces with two components, a debris index and calculus index, to create a numerical determination of the overall oral hygiene. The Simplified index uses the same criteria to assign scores of 6 tooth surfaces (labial) instead of 12.⁴

Because this index is meant for adults, the OHDC modification of the OHI-S for young children scores 4 buccal (facial) tooth surfaces of the primary maxillary incisors, (d, e, f, and g also known as 52, 51, 61, 62 in the international tooth numbering system), denoted OHI-MIS. The OHI-MIS score will be determined after using plaque disclosing liquid which tints the plaque red making it visible. Then an extra-oral photographic image of the buccal (facial) surfaces will be taken to allow asynchronous scoring.

Scores	Criteria
0	No debris or stain present
1	Soft debris covering not more than one-third of the tooth surface, or presence of extrinsic stains without other debris regardless of surface area covered
2	Soft debris covering more than one-third, but not more than two-thirds, of the exposed tooth surface
3	Soft debris covering more than two-thirds of the exposed tooth surface

The criteria for classifying each surface for OHI-MIS will be the same as OHI-S.

At least two of the four possible surfaces must be examined for an individual score to be calculated. Partially erupted teeth should not be scored. **The OHI-MIS debris index = (buccal (facial) incisor scores d+e+f+g) / (Total number of examined surfaces)**. With this calculation, the score will range from 0 (best) to 3 (worst). To evaluate such systems for clinical relevance, Wei & Lang suggest "oral cleanliness is considered: 'good' if the score is between 0.3-0.6; 'fair' when it is 0.7-1.8; or 'poor' when the score is between 1.9-3.0."⁴

Procedures

Depending on the age and cooperation of the child, subjects will be reclined in a knee-to-knee position or seated upright. A research assistant will apply two drops of plaque disclosing solution to maxillary incisors with a disposable micro applicator brush with care not to disrupt the plaque biofilm. Plaque disclosing solution will be used per manufacturer's instructions. The specific product for use in this study is 2Tone (Young Dental). Instructions for use can be found on the following site: http://www.youngdental.com/product/2tone-disclosing-solution/# If needed, the child's mouth will be held open with a mouth prop.

The second research assistant will have a portable overhead light and a mobile phone camera (iPhone 7). After completing the disclosing steps and waiting approximately 15 seconds, the second research assistant will take a series of photographs of the teeth at a distance of approximately 18" above the subject. The second research assistant will verify appropriate capture of images. If images do not clearly capture all maxillary incisors with sufficient clarity and light, the images will be repeated.

References

APPENDIX D: CONTACT ATTEMPT AND WINDOW PROTOCOL

CO-OP Chicago

CONTACT ATTEMPT AND WINDOW PROTOCOL

Research Specialist: Data Collection

Windows

Type of Visit	Earliest start	Latest acceptable	
Baseline	NA	NA	
6-month	14 days before	60 days after	
12-month	Date due	90 days after	

Clock starts when randomized.

12-month due date does not change regardless of when 6-month data collection visit completed.

Attempts

- For main outcomes visit: 12-month
 - These are primary outcomes, need to try to get at all costs.
 - Contact every 2-4 days at varying times of day and varying types of mediums for first 2 weeks. Consider then reducing frequency of attempts but do not give up until window closed.
 - If phone not working, or no answer after 5 attempts, stop by home up to 2 times. If can talk with family, great. If not, then drop off letter.
 - If cannot drop off letter or no response to dropped off letter after 1 week, send certified letter.
 - o If no response to anything, at minimum try to call once a week until window closed.
 - o If ultimately family cannot do in person, do via telephone if feasible for family.
 - If phone not working/no answer, attempt to verify address and phone number at the subject's clinic/WIC.
 - If no answer from all phone numbers and letters, attempt to see if any scheduled appointments at subject's clinic/WIC. If yes, try to be at that appointment to talk with family before/after.
 - Track for each attempt
 - Date
 - Day of week
 - Time of day
 - Medium (phone call, text, email, letter, stopped at home) and number/address used
 - Comment section (note if family answered but can't talk now, family stood you up, talked with other family member and told to call back, etc)
- For 6-month
 - Same as 12-month but shorter window.

CHWs

Windows

4 visits over 12 months, preferred in person at home or other location face-to-face. Goal is 2 visits in first 6 months, 2 visits in second 6 months. Follow-up phone calls should be conducted after visits (total of 4).

- Additional contacts acceptable but not encouraged.
- CHW can call family to schedule as soon as randomization completed.
- Goal is one visit every 2-3 months
- No more than 2 in-person visits before the six month mark; no more than 2 in-person visits after the six month mark
- In-person visits cannot be closer than 30 days.

Attempts

- Contact every 2-4 days at varying times of day and varying types of mediums for first 2 weeks. Consider then reducing frequency of attempts to weekly for 4 weeks, then monthly.
- If phone not working, or no answer after 5 attempts, stop by home up to 2 times. If can talk with family, great. If not, then drop off letter.
- If phone not working/no answer, can verify address and phone number in subject's clinic/WIC.
- If no answer from all phone numbers and letters, look if any scheduled appointments at the clinic/WIC. If yes, try to be at that appointment to talk with family before/after.
- If no answer from all phone numbers and letters and has an identified provider, talk to providers and/or staff at the clinic/WIC to see if they know better way to contact the subject. Ask them to help in process.
- Send certified letter
 - Track for each attempt
 - Date
 - Day of week
 - Time of day
 - Medium (phone call, text, email, letter, stopped at home) and number/address used
 - Comment section (note if family answered by can't talk now, family stood you up, talked with other family member and told to call back, etc)

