5.4 Treatment Assignment Procedures

Participant treatment assignments are determined by their site of enrollment. Sites will be cluster randomized to CHW or usual care. This process is described in Section 5.4.1.

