5.4.1 Randomization Procedures

Clinic and WIC sites will be randomized on the site level once enrollment has reached approximately 90% of goal (18-23 families) at each site. Simple cluster randomization with relatively small numbers of clusters is susceptible to baseline imbalance with

respect to cluster and participant characteristics between the intervention and comparison conditions. Thus, restricted randomization of clusters is commonly employed to enforce greater balance, which both eliminates potential bias and enhances power. We are using terminology from the review paper by Noah Ivers et al. where minimization and covariate-constrained randomization are special cases of a more general category of restricted randomization.³⁷ We will employ a stratified by clinic/WIC minimization method to ensure baseline characteristic balance at both cluster and participant level. Randomizing sites after approximately 90% of the enrollment goal will ensure blinding of RAs, site staff, and participants until most participants from each site are enrolled. (The last 10% of participants are often the slowest to recruit and this small number should not influence the participant-level covariate balance.) Cluster-level summary statistics regarding race and ethnicity characteristics of the site population (African American, Latino, or mixed) and site size (high, medium, low) will be used as cluster-level covariates for minimization. Clusterlevel randomization will be done by the UCSF Coordinating Center (CC). Once a site is randomized, the CC will inform the UIC project manager who will inform the site leadership of the site assignment via email and/or phone call. The UIC project manager will assign a CHW if randomized to that arm. The project manager will then inform the CHW of his/her participants and provide access to their contact information. UIC will send letters via mail to participants informing them of their site's assignment, and their CHW's information if applicable.

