7.2 Enrollment/Baseline Visit with RA (Visit 1, prior to Randomization)

- Obtain and document consent from subject on study consent form.
- Verify inclusion/exclusion criteria.
- Obtain self-reported data via verbal questionnaire. This includes demographic information, oral health behaviors, oral health risk factors, medical history questions, and family psychosocial functioning.
- Weigh child.
- Apply disclosing solution to child's teeth and obtain photographs for plaque assessment.
- If conducted in home, observe child brushing teeth and brushing equipment.
- Explain to family the randomization process and when intervention will start (Intervention will begin after randomization for families in sites that are randomized to receive CHW services. For families in sites that are randomized to not receive CHW services, they will be offered CHW services after study completion in one year.)
- Verify contact information.
- Thank family. Offer remuneration and give flyer on basic oral health recommendations.

7.3 Randomization, Day 0

Each site will be randomized to CHWs or usual care once recruitment is completed or near completion. See Section 5.4.1. for details.

7.4 Intervention in-person visits for CHW-sites only, start Day 1 and complete by Day 365

Four in-person visits will be offered to families. See Appendix D for details. The first two visits will be delivered between days 1-179. The third and fourth visits will be delivered between days 180-364.

7.5 Intervention telephone follow-ups for CHW-sites only, start Day 2 and complete by Day 365

Four follow-up telephone calls will be offered to families. The plan is for follow-up telephone calls to follow in-person visits.

7.6 6-Month Visit with RA, Day 180 (- 14 days, + 60 days)

- Obtain self-reported data via verbal questionnaire. This includes demographic information, oral health behaviors, oral health risk factors, medical history questions, and family psychosocial functioning.
- Weigh child.
- Apply disclosing solution to child's teeth and obtain photographs for plaque assessment.
- If conducted in home, observe child brushing teeth and brushing equipment.
- Record adverse events as reported by subject or observed by investigator.
- Verify contact information.
- Thank family. Offer remuneration.

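### The 6- and 12-month visits are dated from site randomization, so a family enrolled after its site is randomized would fall due early, counted from its own baseline

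*Combined protocol and SAP*

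**What the plan says.** Four parts of the protocol bear on this.

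- **Time origin.** Section 7.3 labels randomization as Day 0. The unit randomized is the site, and families have no randomization date of their own: "Participant treatment assignments are determined by their site of enrollment" (Section 5.4). Appendix D, under the research specialist's data-collection windows, states "Clock starts when randomized".
- **Visits counted from it.** Sections 7.6 and 7.7 and Appendices A and D place the 6-month visit at Day 180 (−14, +60) and the final visit at Day 365 (−0, +90). Appendix D adds "12-month due date does not change regardless of when 6-month data collection visit completed". The community health worker (CHW) visits have their own day counts in Section 7.4 ("The first two visits will be delivered between days 1-179", with the third and fourth visits in days 180–364) and in Appendix A.
- **When a site is randomized.** Section 5.4.1 says "Clinic and WIC sites will be randomized on the site level once enrollment has reached approximately 90% of goal (18-23 families) at each site" and remarks "The last 10% of participants are often the slowest to recruit". Section 7.3 is looser: "Each site will be randomized to CHWs or usual care once recruitment is completed or near completion".
- **Passages pointing the other way.** Section 4 randomizes a site after its recruitment is complete, although a later bullet there asks only for sufficient enrollment. The Section 7.2 heading and the baseline column of Appendix A place the baseline visit before randomization. Section 4 also gives every participant 12 months (+3) of study procedures.

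No passage gives a family enrolled after site randomization its own Day 0.

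**The concern.** If Section 5.4.1 is followed, the last families at a site consent after their clock has started. Their 6- and 12-month visits then fall due early, counted from their own baseline. In the CHW arm, the calendar time in which the intervention could act before the outcome is also shorter than for other families.

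The primary objective concerns a one-year intervention, and Section 12.3 makes the arm-by-time interaction the focus of the analysis. A late family's measurements would enter that model as ordinary 6- and 12-month occasions. The shortened follow-up affects both arms; the shortened opportunity for exposure affects only the CHW arm and pulls the contrast toward zero. Staff who must compute a due date for such a family have only the site-level rule, which was not written with that family in mind.

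**Working it through.** **The plan's own windows.** Day 180 − 14 = Day 166 and 180 + 60 = Day 240. Day 365 − 0 = Day 365 and 365 + 90 = Day 455. Sections 7.6 and 7.7, Appendix A and Appendix D agree on these.

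**How many families.** Section 4 and Section 5.3 give 420 families, 18–23 at each of 20 sites. Section 5.4.1 leaves about 10% to enroll after randomization: 0.10 × 420 = 42, or 1.8–2.3 per site. This is nominal and an upper figure, since Section 7.3 also allows randomization after recruitment is complete.

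**Effect on due dates.** Let L be the days from site randomization to a late family's baseline. L is an assumption, because the documents do not give it. Counted from that family's baseline, visits are due at 180 − L and 365 − L days, and the windows run from 166 − L to 240 − L and from 365 − L to 455 − L.

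| Assumed L | 6-month due | 6-month window | 12-month due | 12-month window closes |
|---|---|---|---|---|
| 30 | 150 | 136–210 | 335 | 425 |
| 60 | 120 | 106–180 | 305 | 395 |
| 90 | 90 | 76–150 | 275 | 365 |
| 120 | 60 | 46–120 | 245 | 335 |

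A visit a full 365 days after baseline is still allowed when 455 − L ≥ 365, that is, for L ≤ 90.

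**What is plausible for L.** There are two hints, and neither is a bound. Section 4 keeps two months of recruitment slack. At an assumed even pace of 21 families in 10 months, the last 2.1 families take 10 × 2.1/21 = 1 month; Section 5.4.1 expects them to be slower than that.

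**Can four CHW visits still occur?** Section 7.4 puts two visits in days 1–179 and two in days 180–364; Appendix D requires at least 30 days between visits. With a first visit possible on Day L + 1, the second falls on Day L + 31 at the earliest, and L + 31 ≤ 179 gives L ≤ 148. The second-half pair then still fits. Four visits are therefore feasible at every lag in the table.

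**Dilution.** Assume effect is proportional to exposure time. The loss per late family is L/365: 8%, 16%, 25% and 33% for the four lags. Over the whole arm, multiply by 0.10: 0.8%, 1.6%, 2.5% and 3.3%.

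**Power for plaque.** This is a simple two-group approximation with difference 0.31, SD 0.78, two-sided alpha 0.025, 15% attrition applied once, and design effect 1 + 20 × 0.01 = 1.20. At 210 per arm the effective number is 210 × 0.85/1.20 = 148.75 and power is 0.88.

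- If late families keep 75% of the effect (the 90-day case), the difference is 0.31 × (1 − 0.10 × 0.25) = 0.302 and power is 0.86.
- If they keep only half, the difference is 0.31 × (1 − 0.10 × 0.50) = 0.2945 and power is 0.85. Under proportionality this would need a lag of about 0.5 × 365 ≈ 182 days, beyond any in the table.
- At the plan's minimum of 170 per arm, that harsher case takes power from 0.80 to 0.75.

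**The case against.** The strongest reply is that late enrollment may not be intended at all. Section 4 completes a site's recruitment before randomizing it, and Section 7.2 and Appendix A place baseline before randomization. On those passages L never arises. This stands as a limit: the problem follows from Section 5.4.1, and the documents disagree among themselves. It does not remove the point, because Section 5.4.1 is the section that governs randomization and it plans for these families explicitly.

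Four stronger readings are tempting, and the documents do not support them.

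- *That late families cannot receive the intended number of visits.* Section 2.2 describes the dosage as four in-person visits within one year, and four remain feasible up to a lag of about 148 days. Nothing in the documents suggests lags that long.
- *That Appendix D starts the CHW clock at randomization.* The clock sentence stands only under data collection. The CHW block in Appendix D does not define the origin of its six-month mark; the CHW day counts come from Sections 7.4 and 7.5 and Appendix A.
- *That late families are necessarily followed for less than a year.* With lags up to 90 days the window still admits a 365-day visit. It is the due date that comes early.
- *That late families are the only ones whose interval from baseline is off.* The other 90% or so have the opposite distortion. They wait for randomization for a time that Section 5.3 acknowledges without a stated maximum, so their 12-month visit falls due more than 365 days after baseline.

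**Conclusion.** The point holds in a limited form and is minor. As written, Section 5.4.1 combined with the site-level Day 0 gives up to about 10% of families (nominally 42) a 12-month due date L days early relative to their own baseline. The date arithmetic is exact; the lag is assumed. The dilution of about 1–3% rests on lags of 30–120 days and on effect being proportional to exposure time, which the documents neither state nor exclude. The loss of power is correspondingly small, and the sample size need not change. What warrants action is that the rule gives a worse result than an almost free alternative, and that the sections conflict on whether such families exist.

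**What to change.** In Section 7.3 and in the data-collection part of Appendix D, define each family's Day 0 for the 6- and 12-month due dates, in both arms, as the later of site randomization and that family's baseline visit. Applying it in both arms keeps outcome timing comparable.

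The cost is a sentence in each place and a change to the due-date calculation. The few late families finish later by their lag.

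This equalises the time from first possible exposure to outcome. It does not equalise baseline-to-outcome time for families who wait for randomization, and the text should not claim that it does.

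For the CHW visit windows, Sections 4, 5.4.1 and 7.2–7.5 and Appendices A and D contradict each other on whether late enrollees exist, and leave open how their intervention year is counted. The sponsor must reconcile these passages. This is best done together with the due-date change, so that the two origins for a late family are set knowingly.

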APPENDIX E: CHW ACTION PLAN

COordinated Oral Health Promotion (CO-OP) Chicago

ACTION PLAN / PLAN DE ACCIÓN

Date:

Fecha:

In the next _____, we are going to: *what* En las próximas _____, vamos a:

We will do this: when

Vamos a hacerlo: cuando

The following things may get in the way of our plan:

Es posible que las siguientes cosas puedan interferir en nuestro plan:

We will try to get past these barriers by:

Vamos a tratar de superar estos obstáculos:

Level of confidence/Nivel de seguridad:

1	2	3	4	5	6	7	8	9	10
Not v	ery sure							Ve	ery sure
No es	tamos seg	guros					Es	stamos mu	ly seguros

Signature of participant Firma de participante Signature of CHW Firma de promotora/e

APPENDIX F: CARIES RISK ASSESSMENT

Caries Risk Assessment

American Academy of Pediatric Dentistry. Guideline on caries-risk assessment and management for infants, children, and adolescents. Pediatric Dentistry. 2013 Sep-Oct;35(5):E157-64.

Complete for each person present if family agrees.

Children ages 0-5 years old

Date: CHW: Child ID number (or initials and age if not index child):

	High Risk	Low Risk
Biological		
Mother/primary caregiver has active caries	Yes	
Family is low income	Yes	
Child has more than 3 between meal snacks or beverages that	Yes	
contain sugar per day		
Child is put to bed with a bottle containing natural or added sugar	Yes	
Child has special healthcare needs	Yes	
Child is a recent immigrant	Yes	
Protective		
Child receives fluoridated drinking water or fluoride supplements		Yes
Child has teeth brushed daily with fluoride toothpaste		Yes
Child receives topical fluoride from health professional		Yes
Child has dental home/regular dental care		Yes
Clinical Findings*		
Child has white spot lesions or enamel defects	Yes	
Child has visible cavities or fillings	Yes	
Child has plaque on teeth	Yes	

* CHWs should only do what they feel comfortable with and what family is comfortable with, can skip this section

APPENDIX G: CORE CURRICULUM DELIVERY GUIDE

CO-OP CHICAGO CHW HOME VISIT Core Curriculum Delivery Guide

FIRST VISIT

Goals:

- Get to know the family
- Find out what they want to get out of the project or work on first
- Make a plan for the next 3 visits
- Begin or complete one core curriculum module

What to bring:

- CHW Training Manual (with ppt slides)
- Caries Risk Assessment forms
- Action plans
- Laptop/tablet with hotspot
 - 1. Introduce yourself and tell a little about yourself.
 - 2. Ask about them: general and then why they joined program
 - a. What do they want to work on the most in the next year?
 - b. What are the biggest oral health concerns they have?
 - 3. Caries Risk Assessment for all family members participating a. Discuss scores
 - 4. Get an idea about what they know, where they are at
 - a. Oral health basics module
 - 5. Make a plan for the next several visits about what content areas you will cover.
 - a. Talk about what we have to offer
 - b. Match what they are interested in with the content areas
 - c. Outline plan for next 3 visits
 - 6. Introduce action plans
 - a. What they are, how they work, why we do them
 - b. What does family want to change before next visit?
 - c. Help family make action plan
 - d. Give copy to participant
 - 7. Plan for next visit
 - a. Work with family to decide on a time for next visit

SUBSEQUENT HOME VISIT PROTOCOL

- 1. Greetings 5 minutes
- 2. Review action plan 10 minutes
 - a. Discuss if action plan achieved. If yes, how. If no, why not and speculate on ways to achieve the plan in the future.
 - b. Discuss belief in ability to change behaviors
- 3. Core Curriculum 30 minutes
- 4. Action plan 10 minutes
 - a. What does family want to change?
 - b. Help family make action plan
- 5. Plan for next visit 5 minutes
 - a. Work with family to decide on a time for next visit

TELEPHONE FOLLOW-UP VISITS

- 1. Greetings 1 minute
- 2. Ask if any questions since last visit, discuss up to 15 minutes
- 3. Review action plan, revise if needed up to 10 minutes
- 4. Remind about next visit, confirm date, time, place up to 5 minutes

Content Areas

Core Curriculum

- 1. Oral health basics
- 2. Tooth brushing
- Fluoride
 Weaning
- 5. Nutrition
- 6. Seeing the dentist

Materials list

- CHW Training Manual (with ppt slides)
- A Pediatric Guide to Children's Oral Health Flip Chart and Reference Guide
- NIDCR one-pager "A Healthy Mouth For Your Baby"
- Mouth with teeth Model
- Toothbrushes
- Floss
- Toothpaste
- Sippy cups
- Dental referral list
- Laptop/tablet with hotspot
- Business cards
- Project info and contact sheet
- Optional: food and drink containers

Depending on the content area, use the following pages as a guide.

Oral Health Basics

i. Goals:

- 1. To define dental caries
- 2. To describe causes of caries.
- 3. To discuss importance of caries prevention.
- *ii. What you need:*
 - 1. CHW Training Manual (with ppt slides)
 - 2. A Pediatric Guide to Children's Oral Health Flip Chart and Reference Guide
 - 3. Mouth with teeth model
 - 4. Handout: NIDCR one pager "A Healthy Mouth For Your Baby"
- A. Topic areas
 - a. Present normal infant tooth development: "A Pediatric Guide to Children's Oral Health Flip Chart and Reference Guide" pages 2-3, mouth with teeth model
 - b. If family interested, can present normal tooth anatomy: CHW Training ppt slide 10-11
 - c. Ask caregiver to list causes of caries.
 - i. Define caries: "A Pediatric Guide to Children's Oral Health Flip Chart and Reference Guide" page 5
 - d. Ask caregiver to identify behaviors that could cause caries.
 - i. Discuss all behaviors: "A Pediatric Guide to Children's Oral Health Flip Chart and Reference Guide" pages 6-9.
 - ii. Make sure discuss
 - 1. Vertical transmission (caregiver to child from utensils, pacifiers, sharing food)
 - 2. Family history of caries
 - 3. Frequency foods/drinks without enough breaks
 - 4. Sleeping with a bottle or cup
 - 5. Sugary foods/drinks
 - 6. Gummy foods
 - 7. Some medical conditions (that impair child's saliva, ability to participate in brushing, or require special medicines)
 - iii. If family interested, can discuss bacteria and how bacteria interact with sugar to form caries
 - e. Describe different stages of tooth decay (i.e. white spots, brown spots)
 - i. Show pictures: "A Pediatric Guide to Children's Oral Health Flip Chart and Reference Guide" page 6, CHW Training ppt slide 12, 19, 24-26
 - f. Discuss importance of caries prevention, emphasize they can prevent caries from happening and stop those that have already started (CHW will explain how)
 - i. Give handout "A Healthy Mouth For Your Baby"

2. Brushing Basics

- i. Goals:
 - 1. Describe when to start brushing teeth (or wiping gum line)
 - 2. Describe how and when to brush teeth
 - 3. Describe types of toothbrushes
 - 4. Describe types and amount of toothpaste
 - 5. Explain how to floss

ii. What you need:

- 1. CHW Training Manual (with ppt slides)
- 2. Mouth with teeth model and toothbrush
- 3. Toothpaste (for demonstration of quantity)
- 4. Laptop/tablet with hotspot

A. Topic areas

- a. Discuss when caregiver should start wiping gum line or brushing child's teeth
- b. Discuss how often to brush
 - i. If needed, discuss strategies to remember
- c. Show caregiver on model teeth how to brush
 - i. Discuss brushing technique
 - ii. Discuss brushing duration
 - iii. If needed, discuss strategies to help (timers, songs, etc)
- d. Show caregiver photo on how much toothpaste to use (CHW Training Manual ppt slide 45). Could also show on real toothbrushes.
- e. Show video on tooth brushing based on child's age (i.e. baby vs toddler)
 - i. Baby:
 - 1. https://www.youtube.com/watch?v=kyJo7vUpbT8
 - 2. https://www.youtube.com/watch?v=KB8mwBfcrXw
 - ii. Child:

http://www.colgate.com/en/us/oc/oral-health/basics/brushing-and-flossing/video/No-More-Nasties-Brushing-for-Kids

- iii. Adult: https://www.youtube.com/watch?v=ImmFRJjadOI&index=3&list=PLEbUg8bEgm RWGhvM1KgvX9bA FkbG9WEM
- f. Discuss different types of toothbrushes
- g. Discuss roll of spitting
- h. Show caregiver how to floss teeth and when to start
- i. Talk about how to store toothbrushes
- j. Practice brushing (and flossing if family wants)

3. Fluoride

i. Goals:

- 1. To know what fluoride is and how it prevents cavities
- 2. Understand fluoride recommendations for toothpaste
- 3. To know benefits of fluoridated water (tap water) as opposed to bottle water
- 4. To know why fluoride varnish is applied
- 5. Dispel fluoride myths
- ii. What to bring:
 - 1. CHW Training Manual (with ppt slides)
 - 2. Different kinds of toothpaste (infant, child, adult regular, no fluoride adult)

- a. Ask if caregiver knows what fluoride is
 - i. Discuss what it is and why it is important.
 - 1. Makes teeth stronger to resist caries
 - 2. Can rebuild teeth when some damage
 - 3. Has some anti-bacterial properties
- b. Identify day-to-day activities that provide teeth with fluoride
 - i. Toothpaste
 - 1. Ask what kind of toothpaste they use for themselves and children, and why
 - 2. Explain recommendation for fluoride toothpaste
 - 3. Practice reading labels to identify fluoride
 - ii. Water
 - 1. Ask if they know about fluoride in water
 - 2. Discuss types of water they drink (bottled, filtered, tap)
 - a. Explain amount of fluoride in those
 - b. If no fluoride in source of water, explain how to fix that (change type of water or add fluoride)
- c. Ask if families have received fluoride varnish
 - i. Show picture (CHW Training manual ppt slide 40) or show demo varnish kit
 - ii. Discuss where and when to get (i.e. dentist and/or pediatric office)
- d. Discuss concerns for too much fluoride, provide reassurance

4. Weaning

- i. Goals:
 - 1. To identify age when child should transition from bottle to cup
 - 2. To identify sippy cup recommendations
 - 3. To discuss effects of nighttime feeding
- *ii.* What to bring:
 - 1. CHW Training Manual (with ppt slides)
 - 2. A Pediatric Guide to Children's Oral Health Flip Chart and Reference Guide
 - 3. Consider bringing different kinds of sippy cups (hard top, soft tops)

- a. Ask about sleeping with the bottle or cup
 - i. Discuss recommendations: never allow sleeping with bottle/cup
 - ii. Remind families consequences, review baby bottle caries if needed
 - iii. Discuss challenges encountered and strategies
- b. Ask caregiver to state the age in which a child should transition to a cup
 - i. Discuss recommendations: Change over to sippy cup/regular cup at 1
 - ii. Remind families consequences, review baby bottle caries if needed
 - iii. Discuss challenges encountered and strategies
- c. Discuss types of sippy cups
 - i. Explain why hard top cups preferred

5. Nutrition

i. Goals:

- 1. To identify foods that contribute to caries
- 2. To identify beverages, including juice, that affect oral health
- 3. To identify effects of frequent snacking
- 4. To identify healthy foods
- ii. What to bring:
 - 1. Consider bringing some juice containers, fruit snacks, gummy vitamins, soda containers to read labels and compare

- a. Ask caregiver what food or beverage items can cause caries. In discussion:
 - i. Emphasize sugar-sweetened beverages (avoid)
 - 1. Sodas also have acid which hurts teeth
 - ii. Discuss juice (sugar in natural pure juice is still sugar, don't recommend)
 - iii. Gummies, fruit snacks, and sticky foods (avoid)
 - iv. Candy (avoid)
 - v. Discuss milk and breastfeeding (sugar in milk too, need to clean teeth afterwards)
- b. Discuss caregiver about frequent snacking and how it contributes to caries
 - i. Frequent foods but more likely frequent drinking (includes milk/breastmilk)ii. Emphasize breaks in feeding
- c. Discuss strategies for limiting sugar-sweetened beverages, unhealthy snacks, and frequency
 - i. Kids want to do what their parents do...
 - ii. Engage family in discussion,
- d. Inform caregiver what food items are healthy for child
 - i. Foods that clean the teeth while eating them
 - 1. Fresh fruits and vegetables
 - 2. Crunchy foods (apples, pears, carrots, salads, etc)
 - ii. Variety

6. Seeing the Dentist

i. Goals:

- 1. To know when a child should see a dentist
- 2. What to expect at first dental visit
- 3. How often should child go to dentist
- 4. To know the responsibility of a medical provider in oral health

ii. What to bring:

1. Dental referral list

- a. Discuss when a child should start going to the dentist and why
 - i. At 1 year of age or within 6 months of getting first tooth
 - ii. Why: Start fluoride, receive education, identify any problems, get child used to the dentist
- b. Identify/list what will happen at first dental visit
 - i. Teeth examined
 - ii. Fluoride applied
- c. Discuss how often child should go to dentist
 - i. Every 6 months
- d. Discuss challenges to bring child to dentist, and problem solve
 - i. Insurance (Medicaid covers dental for children but not all dentist accept it)
 - ii. Finding dentist that will take babies
 - 1. Dental referral list
 - iii. Scheduling
 - iv. Transportation
 - v. Child resistance or fear
 - vi. Children with special needs
- e. Discuss the role a pediatrician or family doctor has regarding oral health
 - i. Should be screening and can often apply varnish
- f. Ask caregiver if he/she receives dental care and if he/she would like assistance
 - i. Dental referral list
 - ii. Insurance assistance

Version 2.0 19 March 2018

APPENDIX H: C	HW ENCOUNTER TRACKING FORM
	Participant ID
ENC	CHW DUNTER DOCUMENTATION
	SUNTER DOCUMENTATION
Participant Name	Time Encounter Began
Accompanied by: $_1\Box$ no one $_2\Box$ someone (name: _) Time Encounter Ended
Encounter Number (circle one): 1 2 3 4 other	Follow-up call 1 Follow-up call 2 Follow-up call 3 Follow-up call 4
Encounter Location: 1 clinic (specify)) ₂□ WIC (specify) ₃□ home ₄□ other
Date of Encounter:	
CARIES RISK ASSESSMENT	
□ Completed □ Not completed because already done	at past visit 🛛 Not completed for other reason (describe):

CORE CURRICU	DRE CURRICULUM					
TOPIC	Check one	SUBTOPICS	MATERIALS USED	Details and Comments		
1. Oral health basics	\Box Major topic of visit $ ightarrow$	□ Normal tooth development	CHW Training Manual			
	\Box Minor topic of visit \rightarrow	□ Tooth anatomy	\Box A Pediatric Guide to			
	\Box Not covered	\Box What are caries	Children's Oral Health Flip Chart and Reference Guide			
		□ Causes of caries	□ Mouth with teeth model			
		□ Importance of caries prevention	□ A Healthy Mouth For Your			
		□ Other (specify):	Baby handout			
			□ Other (specify):			
2. Tooth brushing	\Box Major topic of visit $ ightarrow$	□ When to start	□ CHW Training Manual			
5	\Box Minor topic of visit \rightarrow	Frequency	\Box Mouth with teeth model			
	□ Not covered	🗆 Technique	□ Toothbrushes given			
			□ Floss given			
		Equipment	□ Tooth brushing videos			
		□ Toothpaste amount	□ Other (specify):			
		□ Spitting				
		□ Flossing				
		□ Other (specify):				
3. Fluoride	\Box Major topic of visit $ ightarrow$	□ Define fluoride and roles	CHW Training Manual			
	\Box Minor topic of visit \rightarrow	□ Toothpaste	□ Toothpaste			
	□ Not covered	□ Water	□ Other (specify):			

		□ Varnish		
		□ Fluoride risks/myths		
		□ Other (specify):		
4. Weaning	\Box Major topic of visit $ ightarrow$	\Box When to transition from bottle	CHW Training Manual	
	\Box Minor topic of visit \rightarrow	□ Sippy cup recommendations	□ Sippy cups	
	□ Not covered	□ Nighttime feeding	□ Other (specify):	
		□ Other (specify):		
5. Nutrition	\Box Major topic of visit $ ightarrow$	□ Sugar-sweetened beverages	□ Other (specify):	
	\Box Minor topic of visit \rightarrow	□ Juice		
	□ Not covered	□ Sticky foods, candy, etc		
		□ Frequency of foods/drinks		
		\Box Healthy foods		
		□ Other (specify):		
6. Seeing the dentist	\Box Major topic of visit $ ightarrow$	\Box When to start	□ Dental referral list	
dentist	\Box Minor topic of visit \rightarrow	□ What to expect	□ Other (specify):	
	□ Not covered	□ Frequency		
		\Box Role of the pediatrician		
		□ Other (specify):		
7. Other topics		Describe:		
7. Other topics	\Box Major topic of visit $ ightarrow$	Describe.		
	\Box Minor topic of visit \rightarrow			

□ Not covered		
---------------	--	--

ACTION PLAN

Did family accomplish their Action Plan from the last visit?					
□ Yes (exactly as they had planned)					
□ No, not even close. Why?					
□ Some but not all. Why?					

ENCOUNTER PARTICIPATION

Did the target child participate? 1 Yes 2 No If yes	, how much did they participate?	$_1\Box$ A lot $_2\Box$ A li	ttle ₃□ Not at all
List each other person who participate in the visit and the	amount they participated:		
Person 1: First name:	Relationship to child:		Participated: $_1\Box$ A lot
2□ A little 3□ Not at all			
Person 2: First name:	Relationship to child:		Participated: $_1\Box$ A lot
2□ A little 3□ Not at all Person 3: First name:	Relatio	nship to child:	
Participated: 1 A	lot $_2\Box$ A little $_3\Box$ Not at all F	Person 4: First name	:
Relationship to child: _	F	Participated: $_1\Box$ A lot	$_2\Box$ A little $_3\Box$
Not at all Person 5: First name:	Relationship to child:		Participated:
1 □ A lot 2 □ A little 3 □ Not at all Person 6 : First	st name:	Relationship to o	child:

Based on NIDCR Clinical Trial (Interventional) Protocol Template v4.0 - 20140103

COordinated Oral Health Promotion (CO-OP) Chicago Trial Protocol

Version 2.0 19 March 2018

		Participated: ₁□ A lot	2□ A little	₃□ Not at all Person 7: First name:		
		Relationship to child:		Participated: 1 A lot	2□ A little	3
Not at all P	Person 8: Firs	t name:	Relation	ship to child:	Partio	cipated:
1□ A lot	2□ A little	₃□ Not at all				

SELF EVALUATION

Self-Ev	Self-Evaluation – How did I (the CHW) do today?			Н	ow much p	rogress do I feel	l was made on thi	s visit?		
1	2	3	4	5	-	1	2	3	4	-
Poor	Mediocre	Satisfactory	Good	Excellent		None	Some	Good	Great	

List anything else that happened or seems important here:

